## PROTOCOL SYNOPSIS

|                                   |  |
|-----------------------------------|--|
| TITLE                      | PIRFENIDONE FOR RESTRICTIVE ALLOGRAFT DYSFUNCTION (PIRCLAD)   |
| SPONSOR                    | Nina Ireland Program for Lung Health discretionary funds from [name]   |
| FUNDING ORGANIZATION       | UCSF   |
| NUMBER OF SITES            | 1  |
| RATIONALE                  | 
Long-term survival after lung transplant is limited by the development of chronic lung allograft dysfunction. In approximately 30% of cases, chronic lung allograft dysfunction has a restrictive phenotype (RCLAD) characterized by fibrosis with rapid progression. Approximately 60% of patients with RCLAD die within one year from respiratory failure. Currently, there are no therapies available for RCLAD. Due to the similarities between RCLAD and Idiopathic Pulmonary Fibrosis (IPF), there is keen interest in the transplant community to investigate the effect of the anti-fibrotic drug pirfenidone in RCLAD. Pirfenidone has been proved to slow the progression of IPF and is approved by the Food and Drug Administration (FDA) for that indication.
 
This protocol will evaluate the safety and tolerability of pirfenidone in lung transplant recipients with RCLAD. The results of this pilot study will provide the foundation for a multicenter randomized control trial to evaluate the efficacy of pirfenidone in slowing the progression of RCLAD.
 |
| STUDY DESIGN               | Interventional, open-label, pilot study  |
| PRIMARY OBJECTIVE          | Asses the safety and tolerability of Pirfenidone in lung transplant recipients with RCLAD.   |
| NUMBER OF SUBJECTS         | 10   |
| SUBJECT SELECTION CRITERIA | 
Inclusion Criteria:
 
Subjects aged 18 to 80 years old, who underwent bilateral lung transplantation at UCSF and have a diagnosis of RCLAD based on the International Heart and Lung Transplant (ISHLT) classification.
 
The diagnosis of RCLAD is based on spirometry (FEV1 <math>\leq</math> 80% and FVC <math>\leq</math> 80% of best post-transplant baseline) and CT scan (e.g. pleuroparenchymal fibroelastosis) findings.
 
Subjects with steady-state blood concentration of tacrolimus, as
   |

|  |   |
|--|---|
|  | 
assessed by 10-12 hour trough level.
 
Exclusion Criteria:
 
Patients with RCLAD will be excluded if they are, in the judgment of the investigator, unlikely to tolerate pirfenidone. Other exclusion criteria will include:
 

• FVC decline related to non-RCLAD causes (e.g. pulmonary edema, pleural effusion, etc).

• Patients with any severe comorbidity complicating RCLAD which might determine their prognosis and functional level (e.g. active malignant disease) within the last 12 months.

• Patients who have resumed smoking after transplantation.

• Renal insufficiency (creatinine clearance < 30 ml/min calculated by the CKD-Epi formula).

• Total bilirubin above the upper limit of the normal range (ULN), except in patients with predominantly unconjugated hyperbilirubinemia (e. g. Gilbert's disease).

• Aspartate or alanine aminotransferase (AST or ALT) > 3 times the ULN.

• Known allergy of hypersensitivity to Pirfenidone

• Ongoing use or expected use of any of the following therapies:

- Strong inhibitors of CYP1A2 (e.g. fluvoxamine or enoxacin).

- Moderate inhibitors of CYP1A2 (e. g. mexiletine, thiabendazole, or phenylpropanolamine). Ciprofloxacin will be allowed only at doses equal or less than 500 mg BID.

• Inability to provide informed consent.

 |
| TEST PRODUCT,
DOSE, AND ROUTE
OF
ADMINISTRATION   | Pirfenidone 2403 mg/day for 56 weeks. Pirfenidone dose will be titrated up as follows: 801 mg/day (1 capsule, 3 times daily) for 2 weeks, then 1602 mg/day (2 capsules, 3 times daily) for 2 weeks, then 2403 mg/day (3 capsules, 3 times daily) for 52 weeks.  |
| CONTROL
PRODUCT, DOSE
AND ROUTE OF
ADMINISTRATION | N/A   |

|  |   |
|--|---|
| DURATION OF SUBJECT PARTICIPATION AND DURATION OF STUDY | 
Subjects will be in the study for 56 weeks. Subjects that wish to continue taking pirfenidone beyond 56 weeks may be eligible for PIRCLAD extension until September 30, 2021. The Principal Investigator will determine eligibility for PIRCLAD extension on a case by case basis. Subjects must continue to meet the inclusion and exclusion criteria, and continue monitoring with laboratory tests, study coordinator calls, clinic visits, pulmonary function tests, and CT scan imaging.
 
The total duration of the study is expected to be up to 48 months. Fifteen months will be for subject recruitment and an additional 14 months for subject follow-up. Subjects eligible for PIRCLAD extension will have up to 19 months of follow up. The last study coordinator call will be 28 days after the last pirfenidone dose.
   |
| CONCOMITANT MEDICATIONS                                 | 
Patients will continue their current immunosuppression regimen consisting of prednisone, mofetil mycophenolate, tacrolimus and sirolimus.
 
Strong inhibitors of CYP1A2 (e.g. fluvoxamine or enoxacin) and moderate inhibitors of CYP1A2 (e. g. mexiletine, thiabendazole, or phenylpropanolamine) will not be allowed. Ciprofloxacin will be allowed only at doses equal or less than 500 mg twice daily.
  |
| SAFETY EVALUATIONS
(PRIMARY OUTCOMES)               | 
Tolerability of pirfenidone: The primary outcome will be the number of subjects that discontinue pirfenidone due to a treatment emergent adverse event (TEAE). A secondary outcome will be the proportion of subjects experiencing a TEAE.
 
Tacrolimus dose change: The outcome will be the ratio of tacrolimus-on-pirfenidone to tacrolimus-off-pirfenidone corrected for the subject's specific steady-state tacrolimus concentration. Subjects with steady-state blood concentration of tacrolimus, as assessed by 10-12 hour trough level, will initiate pirfenidone. Tacrolimus trough level will be measured weekly for the first 6 weeks after starting pirfenidone. Another measurement will be done at week 8. Once a therapeutic blood concentration (8-12 ng/ml) is achieved, measurements will be done monthly. First, we will calculate the concentration-to-dose ratio of tacrolimus on and off pirfenidone by dividing the tacrolimus blood concentration by the corresponding total daily dose of tacrolimus for each period. To obtain the conversion ratio, then we will divide the concentration-to-dose ratio for tacrolimus-on-pirfenidone by the concentration-to-dose ratio for tacrolimus-off-pirfenidone ([blood concentration on pirfenidone/daily dose on pirfenidone]/[blood concentration off pirfenidone/daily dose off pirfenidone]).
 |
| EFFICACY EVALUATIONS                                    | 
FVC decline: We will evaluate change in FVC every 3 months after initiation of pirfenidone.
   |

|   |   |
|---|---|
| (SECONDARY OUTCOMES)             | 
Radiographic progression: We will evaluate fibrosis scores on chest CT at RCLAD onset and in the follow up CT scans performed as part of routine clinical care.
   |
| PLANNED INTERIM ANALYSES         | Quarterly   |
|   |   |
| Rationale for Number of Subjects | 
This is a pilot study with the primary outcome of determining pirfenidone tolerability and its effect on tacrolimus dosing. Even with a small cohort, we hypothesize we will be powered to detect a significance difference in tacrolimus dosing. Based on the single report of tacrolimus dosing increase of 2.5 fold, and conservatively estimating a standardized effect size of 1 (doubling of tacrolimus dose and a standard deviation of the change of 50%), a sample of 8 subjects would be required to detect a significant difference, assuming a two-sided <math>\alpha</math> of 0.05 and <math>\beta</math> of 0.20.
 |
|   |   |

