## 3 STUDY OBJECTIVES

### 3.1 Primary Objectives

The primary objectives of this proposal are to assess tolerability of pirfenidone and determine its impact on tacrolimus blood concentration.

BOS      RCLAD / RAS

[figure not shown]
[figure not shown]

Fig 1. Restrictive Allograft syndrome (RAS). 3.

We hypothesize that treatment-emergent adverse effects (TEAE) in lung transplant recipients will be similar to subjects with IPF, leading to drug discontinuation in the same proportion of subjects.

Based on available literature, we hypothesize that initiation of pirfenidone will be associated with an increase in tacrolimus dose.

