## 6 STUDY PROCEDURES AND GUIDELINES

A Schedule of Events representing the required testing procedures to be performed for the duration of the study is diagrammed below.

| Week                   | 1 | 2 | 3 | 4 | 5 | 6 | 8 | 12 | 16 | 20 | 24 | 28 | 32 | 36 | 40 | 44 | 48 | 52 | 56 | 57 | 60 |
|------------------------|---|---|---|---|---|---|---|----|----|----|----|----|----|----|----|----|----|----|----|----|----|
| Start Pirfenidone      | x |   |   |   |   |   |   |    |    |    |    |    |    |    |    |    |    |    |    |    |    |
| Study coordinator call |   | x |   | x |   | x |   | x  | x  | x  | x  | x  | x  | x  | x  | x  | x  | x  | x  | x  |    |
| Tacrolimus level       | x | x | x | x | x | x | x | x  | x  | x  | x  | x  | x  | x  | x  | x  | x  | x  | x  | x  | x  |
| Liver function tests   |   |   |   | x |   |   | x | x  | x  | x  | x  |    |    | x  |    |    | x  |    |    |    |    |
| Clinic visit           |   |   |   |   |   |   | x |    |    | x  |    |    | x  |    |    | x  |    | x  |    |    |    |
| FVC measure            |   |   |   |   |   |   | x |    |    | x  |    |    | x  |    |    | x  |    | x  |    |    |    |
| CT scan                |   |   |   |   |   |   |   |    |    |    | x  |    |    |    |    |    |    |    |    |    |    |
| Stop Pirfenidone       |   |   |   |   |   |   |   |    |    |    |    |    |    |    |    |    |    |    |    | x  |    |

Prior to conducting any study-related activities, written informed consent must be signed and dated by the subject.

Any clinically significant findings will be communicated to the patients and, with their consent, to the patients' clinical providers.

**Study coordinator call:** Our study coordinator will contact subjects by phone every 2 weeks for the first 6 weeks to inquire about treatment-emergent adverse events (TEAE) and then monthly. TEAE will be recorded and graded according to the Common Terminology Criteria for Adverse Events (CTCAE) v3.0^21. The last phone call will be 28 days after the last pirfenidone dose. Subjects will be provided a phone number to report any additional TEAE. A Data Safety Monitoring Board will be convened.

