#### **STOPPING RULES**

On section 5.4.2.1 "Overview of Adverse Events" of the Investigator's Brochure provided by Genentech it states that almost every patient in both the pirfenidone and placebo treatment groups experienced an adverse event (AE) (99% and 97.9%, respectively). A total of 42.7% of patients in the pirfenidone treatment group had an AE that led to a dose reduction or interruption of any duration compared to 16.2% of patients in the placebo groups; a much lower percentage discontinued treatment early (14.6%) due to any AE. Overall 71 patients died. Fewer patients died in the pirfenidone group than in the placebo group (27 patients, 4.3% vs 44 patients, 7.1%). The treatment group difference was driven in part by a reduction in deaths due to IPF in the pirfenidone-treated patients (10 patients, 1.6% vs 21 patients, 3.4%). On section 5.4.2.5 "Adverse Events Leading to Early Discontinuation of Study Treatment" it states that 14.6% of subjects discontinued treatment due to an AE in the pirfenidone group, compared to 9.6% in the placebo group. Most patients discontinued the treatment in the first year.

Our null hypothesis is that tolerability of pirfenidone in the PIRCLAD study will be similar to that in the PIPF-004, PIPF-006 (CAPACITY), and PIPF-016 (ASCEND) studies. Therefore, we expect the proportion of subjects enrolled in the PIRCLAD study will be similar pirfenidone early due to an AE will be the same or lower. Given the small sample size of the PIRCLAD study, we calculated the maximum early discontinuation proportion that would be similar to 14.6% considering a  $p<0.05$  for statistical significance. This proportion is 25% of study participants ( $p=0.0451$ ), which would be consistent with the findings of the PASSPORT study. The PASSPORT study, a multicenter, prospective, observational post-authorization study that evaluated long-term safety of pirfenidone found that in real-world practice, AE lead to pirfenidone discontinuation in 28.7% (290/1009) of patients, after a median of 99.5 days.

Thus, we expect that up to 3 of the 10 subjects in the study will discontinue pirfenidone early due to an AE.

The PIRCLAD study will stop enrolling new participants if more than 3 subjects discontinue pirfenidone early due to an AE.

Participants who are tolerating pirfenidone well and wish to continue taking it will be allowed to remain in the PIRCLAD study.

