**Discontinuation:**

Patients may temporarily suspend all study drugs for up to 28 consecutive days if they experience toxicity that is considered related to study treatment and that requires a study

treatment hold. Patients who miss > 28 consecutive days of scheduled study treatment because of drug-related adverse events will be discontinued from the study. Exceptions may be made after discussions with the investigators, approval by the Medical Monitor, and consistency with the regulations of the Institutional Review Board/Ethics Committee (IRB/EC).

Patients who miss 14 or more days of Pirfenidone should reinitiate treatment by undergoing the initial 4 week titration regimen up to the full maintenance dosage. For treatment interruption of less than 14 days, the dosage prior to the interruption can be resumed.

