## **DOSE MODIFICATIONS**

### **Dose-reduction Procedure for Adverse Event Management:**

If patients experience significant adverse reactions (i.e., gastrointestinal, photosensitivity reaction or rash), they will have the following temporary dose reduction: reduce dose to 267 mg three times daily (801 mg/day) for 14 days, followed by 534 mg three times daily (1602 mg/day) for another 14 days, prior to returning to the protocol dose of 801 mg three times daily (2403 mg/day). If adverse reactions do not resolve with reducing dose to 267 mg three times daily (801 mg/day) for 14 days, patients will discontinue pirfenidone for 14 days. Any return to protocol dose level after dose reduction must follow documentation of resolution of the adverse event and after discussion with the medical monitor.

If a patient exhibits 2-3 times the upper limit of normal (ULN) ALT and/or AST elevation without symptoms or hyperbilirubinemia after starting Pirfenidone therapy, he/she will discontinue Pirfenidone for 14 days and reinitiate treatment by undergoing the initial 4-week titration regimen up to the full maintenance dosage if tolerated and repeat liver chemistry tests are within normal limits. We will exclude other causes, monitor the patient closely, and repeat liver chemistry tests as clinically indicated.

If a patient exhibits >3 times ULN ALT and/or AST elevation he/she will permanently discontinue Pirfenidone and will not be re-challenged with it.

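### After week 8 nothing triggers a tacrolimus level when pirfenidone is held, reduced, re-titrated or stopped early, although the plan expects pirfenidone to raise the tacrolimus dose needed

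*Combined protocol and SAP*

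**What the plan says.** **Sampling.** The Synopsis (Safety Evaluations, tacrolimus dose change) sets weekly troughs for six weeks from the start of pirfenidone, one more at week 8, and then: "Once a therapeutic blood concentration (8-12 ng/ml) is achieved, measurements will be done monthly". The Schedule of Events in Section 6, introduced as showing the "required testing procedures to be performed for the duration of the study", agrees. It marks tacrolimus at weeks 1-6 and 8, every 4 weeks from 12 to 56, and at weeks 57 and 60, with the pirfenidone stop marked at week 57. The extension table runs every 4 weeks to week 128, then 129 (stop) and 132.

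**Expected interaction.** Section 3.1 states: "we hypothesize that initiation of pirfenidone will be associated with an increase in tacrolimus dose". The sample-size rationale (Synopsis and Section 8) cites a "single report of tacrolimus dosing increase of 2.5 fold" and plans on a doubling.

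**Changes in pirfenidone.** The Data and Safety Monitoring Plan, under Discontinuation, says: "Patients may temporarily suspend all study drugs for up to 28 consecutive days if they experience toxicity". It adds: "Patients who miss 14 or more days of Pirfenidone should reinitiate treatment by undergoing the initial 4 week titration regimen". Under Dose Modifications there are three rules:
- For gastrointestinal or skin reactions, 14 days at 801 mg/day and then 14 days at 1602 mg/day, with a 14-day stop if the reaction does not resolve.
- For ALT/AST at 2-3 times ULN, a 14-day stop followed by re-titration.
- For ALT/AST above 3 times ULN, a permanent stop.

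The laboratory work named there is to "repeat liver chemistry tests as clinically indicated". No tacrolimus level is mentioned under Discontinuation, Dose Modifications or Withdrawal.

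**The concern.** The close sampling at the start makes sense only because pirfenidone is expected to change the tacrolimus dose needed. The same reasoning applies in reverse when pirfenidone is withdrawn. A subject whose tacrolimus dose was raised to stay at 8-12 ng/ml still takes that higher dose on the first day of a hold or stop. If the interaction is real and reverses, the trough rises. When pirfenidone is titrated up again, the trough falls, in a lung recipient who depends on it to protect the graft. At the first titration the plan looks weekly; at these later changes it waits for the next 4-week draw. Safety is the primary objective, and the pilot is meant to lead to a multicenter trial that could inherit the gap.

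**Working it through.** **Plan's own figure.** The sample size of 8 reproduces by the normal approximation for a paired comparison with standardized effect 1: (1.960 + 0.842)² / 1² = 7.85, rounded up to 8. This confirms the planning assumption only; nothing below depends on it.

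**Schedule count (Section 6).** Weeks 1-6 (6 levels), week 8 (1), weeks 12 to 56 every 4 weeks (12), weeks 57 and 60 (2): 21 in total. Seven fall by week 8 and four in weeks 1-4. From week 8 to week 56 every gap is 28 days; the last two gaps are 1 and 3 weeks.

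**1. Wait after an unplanned stop.** For a stop at a random time in a 28-day gap, the wait to the next scheduled level is at most 28 days and on average 28/2 = 14. With weekly sampling it would be at most 7 and on average 3.5.

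**2. Chance that a hold contains no scheduled level.** For a hold of L days starting at random on a 28-day grid, P = 1 - L/28.

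| Hold | P(no level) |
|---|---|
| 7 days | 0.75 |
| 14 days | 0.50 |
| 21 days | 0.25 |
| 28 days | 0 (but the level may come near the end) |

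**3. Re-titration.** Four weeks on the 28-day grid contain 28/28 = 1 level. The first titration had 4.

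**4. Planned stop.** Levels at weeks 56, 57 and 60 give gaps of 1 and 3 weeks. If week 57 is the stop day, the first level after stopping comes 60 - 57 = 3 weeks later. In the extension it is 132 - 129 = 3 weeks.

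**5. Possible trough after withdrawal.** Assume the tacrolimus dose was raised by a factor f to hold 8-12 ng/ml, trough is proportional to dose, the interaction reverses fully and the tacrolimus dose is not changed. The trough moves toward f × (8-12).

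| f | Trough (ng/ml) |
|---|---|
| 1.2 | 9.6-14.4 |
| 1.5 | 12-18 |
| 2 (power assumption) | 16-24 |
| 2.5 (cited report) | 20-30 |

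Above f = 1.5, every subject who was in range ends above 12. A reduction to 801 or 1602 mg/day is not full withdrawal, so the change would be smaller.

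**6. How often.** The Stopping Rules report, for the cited IPF trials, that "42.7% of patients in the pirfenidone treatment group had an AE that led to a dose reduction or interruption of any duration". Applied to 10 subjects, this gives 10 × 0.427 = 4.3 expected and 1 - 0.573¹⁰ = 0.996 for at least one. That rate includes brief interruptions and events before week 8, so it overstates the number affected here. For AE discontinuation at 14.6%: 10 × 0.146 = 1.5 expected and 1 - 0.854¹⁰ = 0.79 for at least one.

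**7. Effect on the tacrolimus ratio.** Assume that a subject's ratio averages the 19 levels from weeks 1 to 56, that the true on/off ratio is 0.50, and that one level falls in a hold with ratio 1.0. The mean is (18 × 0.50 + 1.0)/19 = 0.53.

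**The case against.** The strongest reply is that tacrolimus belongs to clinical care. Section 6 has results reviewed daily and doses adjusted by the transplant nurse coordinators. Monthly study meetings discuss each patient, a return to full dose after a reduction goes through the medical monitor, and the ALT/AST rule asks for close monitoring. The schedule is a minimum, and the team may order more. All of this stands, and it is why the point is moderate. But daily review acts on results already drawn, and none of these provisions prompts a draw. Section 4.1 gives the routine frequency as monthly. The same team was in place at the start of treatment, and the plan still wrote in weekly levels there.

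A second reply is that monthly sampling is conditional on a therapeutic level, and that restarting the initial regimen could bring its sampling with it. That is a reasonable reading, but not an explicit one: the restart rule speaks of dose only, and leaving the range is known only after a draw.

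A reader might also infer more than the documents support:
- **That the planned stop goes unmonitored.** It does not: levels at weeks 57 and 60 (129 and 132) partly cover it.
- **That the plan predicts doubled troughs.** The formal hypothesis is only an increase. The doubling is a power assumption based on one report, and 16-24 ng/ml needs every condition in step 5.
- **That the 99.5-day median in the Stopping Rules places holds in the monthly period.** It describes permanent discontinuation in a separate observational study.

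**Conclusion.** The gap is real for holds, dose reductions, re-titration and unplanned stops, and partial for the planned stop. Followed as written, the plan can leave a subject without a scheduled level for up to about 4 weeks after an early stop, or through an entire 14-day hold about half the time. These timing figures rest only on the published schedule and on events starting at random within a 4-week gap. How far the trough would move is uncertain, and the number of subjects affected cannot be fixed from the IPF rates. A reader might infer that the tacrolimus outcome is compromised; the shift from 0.50 to 0.53 in step 7 does not support that. This is a subject-safety point with a cheap remedy, worth considering, and not a flaw in the analysis.

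**What to change.** Add to the Synopsis tacrolimus text and to the Discontinuation and Dose Modifications sections:

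*After a pirfenidone hold lasting 7 days or more, a protocol dose reduction, a restart by re-titration, or a permanent stop, measure the tacrolimus trough within 1 week and then weekly until it is in range on an unchanged tacrolimus dose; then monthly. During re-titration follow the week 1-8 schedule.*

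For a hold, count the week from the first missed dose, so that a level falls due at day 7. Shorter holds trigger nothing. Add one level at week 58 to the Schedule of Events, and at week 130 in the extension.

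**Cost.** A 14-day hold plus 4-week re-titration is 42 days: 42/7 = 6 levels instead of 42/28 = 1.5, so about 4.5 extra. Carrying the start-up schedule on through its weeks 5, 6 and 8 would add about 2 more (3 levels instead of 1). A permanent stop followed weekly for 4 weeks, taken as an example, adds 3 (4 instead of 1). The planned stop adds one per completer, at most 10. If all 4.3 subjects had one 14-day hold with re-titration, the total would be 4.5 × 4.3 + 10, or about 29, against 21 × 10 = 210 scheduled. Repeat events and unplanned stops add to this. The draws use the laboratories subjects already attend, and the sample size does not change.

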## 4 STUDY DESIGN

### 4.1 Study Overview

1) We will screen for eligible subjects using the computer algorithm on spirometry data abstracted from Apex monthly and by suggestion of the transplant pulmonologists. 2) Then, we will review CT scans to adjudicate a diagnosis of RCLAD. 3) Finally, our pharmacist will determine if tacrolimus dose is stable. After these 3 steps are completed subjects will be eligible for the study.

Subjects will be recruited at their transplant clinic visit or by phone if they previously consented to be contacted with new research study opportunities. We will seek to enroll ten subjects, who will receive pirfenidone for 52 weeks, titrated to 2403 mg/day (3 capsules, 3× daily) over a period of six weeks. Genentech has agreed to provide study drug free of cost.

TEAE will be recorded and graded according to the Common Terminology Criteria for Adverse Events (CTCAE) v3.0^21. Our study coordinator will contact subjects by phone every 2 weeks for the first 6 weeks to inquire about TEAE and then monthly. Subjects will be provided a phone number to report any additional TEAE. A Data Safety Monitoring Board will be convened.

As part of their routine post-transplant surveillance, subjects have monthly laboratory testing that includes tacrolimus blood concentration and liver function tests. Therefore, the manufacturer recommendations of monitoring liver function tests monthly for the first six months and then every 3 months while taking Pirfenidone, will be followed.

Subjects will continue their routine care with clinic visits, spirometry and CT as clinically indicated. In our clinical practice, subjects with RCLAD are expected to have a clinic visit and spirometry approximately every 3 months and a CT scan every 6 to 12 months.

If RCLAD subjects in the study undergo bronchoscopy for a clinical indication, bronchoalveolar lavage, biopsies, airway brushes and plasma specimens will be collected in the biorepository for future analysis of changes in pro-fibrotic mediators after initiation of pirfenidone. These specimens will be collected as part of the ongoing "Lung Transplantation: Improving outcomes through the development of a clinical database and biorepository" study number 13-10738. In the future, we plan to explore whether subjects with RCLAD have a greater rate of decline in telomere length in airway epithelial cells compared subjects without RCLAD.

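### The off-pirfenidone tacrolimus value that divides every subject's primary ratio is not tied to a defined draw, and the week-1 level is not required to precede the first dose

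*Combined protocol and SAP*

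**What the plan says.** The Synopsis (Safety Evaluations, Primary Outcomes) defines the tacrolimus outcome as a quotient of two concentration-to-dose (C/D) ratios: "we will divide the concentration-to-dose ratio for tacrolimus-on-pirfenidone by the concentration-to-dose ratio for tacrolimus-off-pirfenidone", written out as "blood concentration on pirfenidone/daily dose on pirfenidone]/[blood concentration off pirfenidone/daily dose off pirfenidone". Each C/D comes from "dividing the tacrolimus blood concentration by the corresponding total daily dose of tacrolimus for each period".

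On levels before the drug, the Synopsis says "Subjects with steady-state blood concentration of tacrolimus, as assessed by 10-12 hour trough level, will initiate pirfenidone", and Section 5.2, criterion 3, makes this an entry condition. Section 4.1 adds that, before eligibility, "our pharmacist will determine if tacrolimus dose is stable". It also says that in routine care "subjects have monthly laboratory testing that includes tacrolimus blood concentration and liver function tests".

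On levels after the start, the Synopsis says "Tacrolimus trough level will be measured weekly for the first 6 weeks after starting pirfenidone", with a further level at week 8 and monthly levels later. In the Section 6 Schedule of Events the row "Tacrolimus level" is marked in every column from week 1 to week 60. Drug start is marked at week 1 and drug stop at week 57. Section 8 names a paired t-test and promises a detailed SAP before the final analysis.

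**The concern.** Every subject's ratio is divided by the off-pirfenidone C/D, so its source matters as much as that of the on-drug levels. The plan gives a formula but does not point to a measurement. More than one value fits the word off, and an analyst could choose among them after seeing the data.

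Two things are at stake. If the week-1 level were taken as baseline but drawn after dosing had begun, part of any effect would already be in the denominator and the ratio would be pulled toward 1. If the denominator were a single trough, its full sampling error would pass into the ratio, although further pre-drug results probably exist in the clinical record. With about ten subjects and no control arm, both are worth preventing when prevention is cheap.

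**Working it through.** **The plan's own figure.** The Synopsis and Section 8 give 8 subjects for a standardized effect of 1, two-sided alpha 0.05 and power 0.80. The normal approximation gives n = ((1.960 + 0.842)/1)² = 7.85, rounded up to 8, so the figure reproduces. An exact paired t calculation needs 10; power is 68.1% at n = 8 and 80.3% at n = 10. This figure does not depend on where the denominator comes from, and the present point does not change it.

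**Count of scheduled levels (Section 6).** There are 21 tacrolimus levels: weeks 1 to 6, 8, 12, every four weeks to 56, then 57 and 60.
- Before the drug-start column: 0.
- In the drug-start column: 1 (week 1).
- In the drug-stop column: 1 (week 57).
- After the drug-stop column: 1 (week 60). The extension table has the same pattern at weeks 129 and 132.

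**Candidates for the off-drug value.**
- *Entry trough or routine monthly troughs.* These are clearly before the drug, but no number or window is set.
- *Week-1 level.* The text counts six weekly levels after the start, and weeks 1 to 6 are exactly six columns, so week 1 reads as on drug. If it is used as baseline instead, nothing places it before the first capsule.
- *Week-60 level.* It is literally off drug for subjects who stop at week 57, but comes about a year later. Subjects who have died, withdrawn or entered the extension do not supply it.

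**Precision, illustration only.** Assume independent log-scale error s per C/D value and three on-drug levels (for example weeks 5, 6 and 8). The measurement-error variance of the log ratio is s²(1/m + 1/3), where m is the number of pre-drug troughs.
- m = 1: s²(1 + 1/3) = 1.33 s².
- m = 3: s²(1/3 + 1/3) = 0.67 s².
- Ratio of SDs: √(0.667/1.333) = 0.707, a fall of 29%.
- SD for s = 0.2, 0.3 and 0.4: 0.23, 0.35 and 0.46 with one trough; 0.16, 0.24 and 0.33 with three.

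This covers measurement error only. To see the effect on the total, suppose the standardized effect of 1 holds with one trough, for a log effect of log 2, and that the within-subject trough CV is 15% to 40%. Moving to three troughs raises the standardized effect to between 1.016 and 1.122. The total SD therefore falls by 1 − 1/1.016 = 2% to 1 − 1/1.122 = 11%, and exact paired-t power at n = 10 rises from 80% to about 82–88%.

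**Bias, illustration only.** Suppose the true ratio is 0.50 (dose doubled at constant concentration) and a share f of the log effect is already present in the value used as off-drug. The observed ratio is 0.50^(1−f) and, with the SD unchanged, the standardized effect is 1 − f.
- f = 0.10: ratio 0.54, power at n = 10 71.7%.
- f = 0.25: ratio 0.59, power 56.2%.
- f = 0.50: ratio 0.71, power 29.3%.

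Without contamination, power is 80.3%. No value of f can be taken from the documents.

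**The case against.** The strongest reply is that the plan does require an off-drug level. The outcome is described as corrected for the subject's own steady-state concentration, and the next sentence has subjects start pirfenidone once steady state is shown by trough. Read together, these point to the pre-initiation trough and its dose. The missing pre-dose column is weak evidence, because the table leaves out eligibility testing generally: its first liver tests are at week 4, although Section 5.3 excludes on bilirubin and transaminases. The promised SAP could also fix the number and window of routine troughs.

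Most of this stands. A reader might infer that no off-drug level exists, or that the denominator must be either contaminated or a single routine trough. The documents support neither. The entry trough is required, monthly levels can supply several more, and nothing limits the denominator to one. On the text's own count week 1 is on drug, so it contaminates the denominator only if someone departs from that reading, and a draw just before the first capsule would be clean. Nor is a post-stop level the only check on attribution, since weekly levels during titration give a within-subject time course.

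Two things are left. No section names the draws, their number or their window. And an SAP written later can select among existing results, but it cannot turn a post-dose week-1 sample into a pre-dose one.

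**Conclusion.** The off-pirfenidone C/D in a primary outcome is not tied to a defined draw. The natural reading is the pre-initiation steady-state trough, but the text also leaves room for the week-1 and week-60 levels. Contamination by an early on-drug level is possible, not shown, and its size cannot be derived from the documents.

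The gain in precision is real but modest. The 29% fall in measurement-error SD holds only if the alternative is a single pre-drug trough, with independent errors and three on-drug levels. Between-subject differences remain, so the total SD falls by less. This is an inexpensive improvement to the design and the definition; it does not invalidate the outcome.

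**What to change.** In the Schedule of Events, mark the week-1 tacrolimus trough as drawn before the first pirfenidone dose, with the weekly on-drug levels following it. In the outcome definition and the SAP, define the off-pirfenidone C/D as the geometric mean of three values: that trough and the last two routine troughs at the stable tacrolimus dose, each divided by its matching daily dose. With monthly testing this uses roughly the two months before the start. Say what is done when fewer than two such routine results exist, and state that levels drawn after pirfenidone is stopped do not enter the denominator.

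The cost is a change of wording, the abstraction of two existing results per subject, and at most one additional routine draw if six weekly on-drug levels are to be kept. No treatment or dose changes. A separate summary of the week-60 C/D, to see whether it returns toward baseline, is optional and not needed to close the gap.
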